## STUDY PROCEDURES/EVALUATIONS

### Study Procedures

- **Physician Visit** – history and physical, vital signs, review of symptoms, concomitant medications, symptom questionnaire and review of medication compliance while on treatment.
- **History and Physical** –
  - **Full H&P** : A full history and physical examination will be performed at the screening visit as well as inpatient visits.
  - **Interim H&P** : An interim history and physical covering liver and medication related symptoms as well as a limited physical exam will be performed during all other visits.
- **Concomitant medication query** (including dose and indication for each). Documentation of concomitant medication, which may be CYP3A, 2C9, and P-gp substrates, will be performed.
- **Hepatitis B Treatment** To prevent the possibility of a hepatitis B flare during the study, all patients will be treated with nucleos(t)ide analogues while on the study (24 weeks of entecavir or tenofovir + lonafarnib/ritonavir/lambda and 24 weeks of entecavir or tenofovir during the post-therapy monitoring phase). Patients who are not on nucleos(t)ide analogues prior to starting lonafarnib/ritonavir/lambda will be started on either entecavir or tenofovir (which are first-line nucleos(t)ide analogues recommended by the AASLD and EASL for the treatment of HBV) prior to instituting HDV therapy (to reduce the risk of a hepatitis B flare). HBV viral loads will be monitored after starting nucleoside analogue therapy at each outpatient visit during the entire course of study participation. Adequate HBV suppression (serum HBV DNA level <20 IU/mL or undetectable) must be achieved on nucleoside analogue therapy prior to starting HDV therapy which will allow for improved determination of response to experimental HDV therapy. Patients will be informed about the possible adverse effects of these medications during their pretreatment clinic visits and via the package insert that is provided with the medication. Patients will also be offered multiple opportunities to ask questions about these medications during their clinic visits. For patients started on

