nucleos(t)ide analogue therapy as a result of their participation in this protocol, the medication will be administered under this protocol after the consent has been signed and eligibility is determined. If the patient has been taking a nucleos(t)ide analogue prior to enrolling in this study, the specific nucleos(t)ide(s) analogue will be continued. The currently approved nucleoside analogues for hepatitis B include: lamivudine, adefovir, tenofovir, entecavir and telbivudine. At the conclusion of participation in this study, subjects that were prescribed nucleoside analogue therapy by their outside practitioners will be continued on therapy (if clinically indicated) and they will receive this therapy from their outside physicians. For subjects that are started on nucleoside analogue therapies for the purposes of participation in this study, nucleoside analogue therapy may be continued after completion of this study if clinically indicated. If this is the case, therapy will be continued under the 91-DK-0214 protocol, with encouragement that therapy should be received from their outside physicians. Otherwise, if not clinically indicated, nucleoside therapy will be discontinued at the conclusion of participation in this study.

- **Symptom Questionnaire** provides information on categorical presence of symptoms as well as their severity, pattern and frequency (Appendix 1)
- **EKG** – Patients will undergo electrocardiogram (EKG) evaluations collected in digital format due to the rare instances of asymptomatic bradycardia, PR prolongation and QT/QTc interval prolongation described in oncologic trials with use of lonafarnib.
- **Imaging**
  - **Ultrasound and Fibroscan** - An abdominal ultrasound with sheer wave elastography and vibration controlled transient elastography (Fibroscan ®) will be performed for clinical staging of liver disease and to evaluate for hepatocellular carcinoma, masses or any other findings that may preclude a safe transjugular liver biopsy with hepatic venous pressure gradient measurements.
  - **MRI** A structural examination of the liver will be performed via magnetic resonance imaging with gadolinium. An MRI without contrast will be performed in the event that contrast cannot be administered.
- **Liver Biopsy with Hepatic Venous Pressure Gradient (HVPG) Measurements**

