## LABORATORY PROCEDURES/EVALUATIONS

- **Baseline Labs** - prothrombin time (PT/INR), partial thromboplastin time (PTT), reticulocyte count, plasma haptoglobin level, anti-HBc.
- **Routine Labs** - complete blood count (CBC with differential), acute care panel (sodium, potassium, chloride, bicarbonate, creatinine, glucose, urea nitrogen, eGFR ), mineral panel (albumin, calcium, magnesium, phosphorus), hepatic panel (alkaline phosphatase, ALT, AST, total bilirubin, direct bilirubin), lipid panel (total cholesterol, triglycerides, HDL, LDL), LDH, CK, serum uric acid and total protein, urinalysis.
- **Monthly Labs** - PT, thyroid panel, pregnancy test
- **Serology Labs** - HBsAg, anti-HBs, HBeAg, and anti-HBe, anti-HDV, quantitative HBsAg levels.
- **Pancreatitis Monitoring:** amylase, lipase
- **Viral Kinetic and Pharmacokinetic Assessment (VK and PK):** includes HDV RNA and HBV DNA qualitative tests via polymerase chain reaction assay (PCR) or a quantitative PCR (qPCR) for viral titer. One red top tube (10 mL) will be obtained and stored in -80 for pharmacokinetic (PK) analysis of lonafarnib, ritonavir and lambda.

- **Reproductive Panel** - In males, AM levels of inhibin B, luteinizing hormone (LH), total and free testosterone, and follicle stimulating hormone (FSH) will be obtained. In females, AM levels of luteinizing hormone (LH), estradiol, progesterone, antimullerian hormone, follicle-stimulating hormone (FSH), dehydroepiandrosterone (DHEA), dehydroepiandrosterone sulfate (DHEAS), testosterone, sex hormone binding globulin (SHBG) and 17-hydroxyprogesterone (17-OHP) will be obtained.
- **Immunological Studies** - 30 - 50 ml of whole blood will be collected for immunological studies at specified time points described in table 1. 5 mm of liver tissue at baseline and end of therapy will also be collected for immunological studies, provided sufficient liver tissue is available after the required amount is obtained for histopathology. An additional pass will not be performed to obtain additional tissue for immunological studies.
- **Research Blood for Storage** - 7 ml of serum will be collected and stored at -80° C in the NIDDK clinical core lab.

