6. HDV RNA
7. HDV and HBV genotyping

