**Baseline Evaluation and Initiation of Treatment (within 6 months of screening)**

If found to be eligible, the patient will be admitted to the NIH Clinical Center and undergo the following evaluation shortly before starting therapy.

If the patient was on HBV therapy prior to consenting to the study, they will continue on treatment for HBV. If the patient was not on HBV therapy, they will start on approved nucleos(t)ide treatment for a sufficient period of time prior to starting study medication in order for to demonstrate adequate suppression of HBV (serum HBV DNA of <2000 IU/mL).

Upon admission the patient will undergo the following:

1. Continuation of HBV therapy
2. MD Visit
3. Routine labs
4. Baseline labs
5. Pancreatic labs
6. Monthly labs
7. Reproductive labs
8. Serology panel
9. Immunological studies
10. Viral kinetics, pharmacokinetics
11. Microbiome studies

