### **Initiation of Treatment**

All patients will be initiated on lonafarnib 50 mg orally twice daily, ritonavir 100 mg orally twice daily and lambda 180 mcg subcutaneously weekly. Eiger BioPharmaceuticals, Inc will supply the lonafarnib, ritonavir and lambda interferon under a clinical trials agreement. Patients will be initiated on therapy one or two days after the liver biopsy and will remain in the clinical center for 72 hours after induction of therapy for observation of side effects, administration of medication, and timed blood draws to facilitate analysis of virological response kinetics and pharmacokinetic analysis. During the admission, frequent blood sampling will be performed (0, 6, 12, 18, 24, 36, 48 and 72 hours after, the first dose) for viral kinetics, pharmacokinetics and storage.

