**Table 1: Study Design**

			Day 0	Study Weeks (+/- 3 days)				Study Weeks (+/-5 days)	
	Study Week/Procedures	Baseline Evaluation	Start Treatment	1, 2, 3	4, 8, 12, 16, 20	24	25, 26	31 28, 32, 36, 40, 44	48
Lonafarnib, Ritonavir, Lambda	HDV Therapy		x	x	x	x			
HBV Flare Prophylaxis	HBV Therapy	x	x	x	x	x	x	x	X
H&P	MD Visit	x		x	x	x	x	x	X
Vital signs									
Review of symptoms									
Concomitant meds									
Symptom Questionnaire									
Review of medication compliance									
CBC + diff	Routine labs	x		x	x	x	x	x	X
acute									
mineral									
lipid									
hepatic									
LDH									
CK									
Serum uric acid									
total protein									
amylase	Pancreatic labs	x		x	x	x			X
lipase									
HBsAg	Serology Panel	x		x	x	x	x	x	X
anti-HBs									
HBeAg									
anti-Hbe									
PT/INR	Baseline Labs	x				x			X
PTT									
Reticulocyte count									
Plasma Haptoglobin									
anti Hbc									
PT	Monthly labs	x			x	x		x	X
Thyroid panel									
Pregnancy test									
Ophthalmology exam	Consults	x				x			X
Reproductive consult									
LH	Reproductive labs - Females	x			x	x		28, 32, 36	X
FSH									
estradiol									
Progesterone									
AMH									
DHEA									
DHEAS									
Androstenedione									

Testosterone									
Free testosterone									
SHBG									
17-OHP									
Inhibin B	Reproductive labs - Males	x			x	x		28, 32, 36	X
LH									
FSH									
Free testosterone									
total testosterone									
30-50 mL serum for immunology.	Immunological Testing	x	0, 24 hours		4, 8, 12	x		28, 32, 36	X
10 mL red top for PK	VK, PK and Storage		0, 6, 12, 18, 24, 36, 48, 72 hours	x	x	x	x	x	X
HBV DNA									
HDV RNA									
7 mL whole blood for storage									
Blood	Microbiome Studies	x			x	x		x	X
Stool									
Dietary questionnaire									
MRI	Imaging	X				x			X
Ultrasound									
Fibroscan									
EKG	EKG	x		x	x	x			X
Transjugular liver biopsy with portal pressure measurements or percutaneous liver biopsy	Liver Biopsy	x							X

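### Adequate HBV suppression before study drug is defined by two limits 100-fold apart (<20 and <2000 IU/mL), and for newly treated patients nothing says which governs

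*Combined protocol and SAP*

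**What the plan says.** The protocol sets out HBV control before study drug in two places.

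- **Study Procedures, Hepatitis B Treatment:** "Adequate HBV suppression (serum HBV DNA level <20 IU/mL or undetectable) must be achieved on nucleoside analogue therapy prior to starting HDV therapy". The same bullet keeps every patient on a nucleos(t)ide analogue throughout the study. Those not already treated start entecavir or tenofovir before HDV therapy, to lower the risk of a hepatitis B flare. The reason given for requiring suppression is that response to the HDV regimen can then be judged better.
- **Baseline Evaluation and Initiation of Treatment:** a patient not on HBV therapy starts an approved nucleos(t)ide for a period long enough "prior to starting study medication in order for to demonstrate adequate suppression of HBV (serum HBV DNA of <2000 IU/mL". For a patient already treated, this section says only: "If the patient was on HBV therapy prior to consenting to the study, they will continue on treatment for HBV".

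No HBV DNA limit for starting study drug appears in the Study Entry Criteria, the Screening list, the HBV DNA assay paragraph, Table 1, or the enrolment and exclusion checklists. The only other use of 2,000 IU/mL is in the lonafarnib risk text under Hazards and Discomforts, where it forms part of the definition of an HBV flare.

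**The concern.** The term, the analyte and the step are the same in both places, but the numbers are not. One text is written as a requirement. The other sits in the schedule section that staff would naturally have open when starting a patient on treatment. Someone working from the schedule section alone could take a newly treated patient at, say, several hundred IU/mL as adequately suppressed, although the Study Procedures text says that patient is not ready.

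What is at stake is whether the condition for first dose is applied in the same way to every patient, and whether the two purposes the protocol gives (lowering flare risk and a clearer reading of response) are served as intended. Following one section as written could also put the trial out of line with another.

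**Working it through.** The protocol gives no derived figure to reproduce. The check compares the two texts and takes the ratio of the limits.

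**Inputs**

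| Item | Study Procedures, Hepatitis B Treatment | Baseline Evaluation and Initiation of Treatment |
|---|---|---|
| Term defined | Adequate HBV suppression | Adequate suppression of HBV |
| Measure | Serum HBV DNA | Serum HBV DNA |
| Step | Before HDV therapy | Before study medication |
| Limit | <20 IU/mL or undetectable | <2000 IU/mL |
| Force | Must be achieved | Purpose of the lead-in on nucleos(t)ide |
| Patients | All, including those newly started | Limit attached to those newly started |

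**Size of the gap**

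- Ratio: 2000 / 20 = 100.
- On the log scale: log10(100) = 2.

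**Outcome for a newly treated patient, by HBV DNA when study drug is due**

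| HBV DNA (IU/mL) | Study Procedures | Baseline section | Consistent? |
|---|---|---|---|
| Below 20, or undetectable | Met | Met | Yes |
| 20 to 1999 | Not met | Met | No |
| 2000 or more | Not met | Not met | Yes |

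The texts disagree only in the middle band, and there they give opposite answers.

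**How many patients fall in that band?** This cannot be derived. The Background says that most patients with delta hepatitis have low HBV DNA, and that about 20% of those seen at this centre have high levels, without defining high. Neither statement describes the level reached on a nucleos(t)ide before study drug.

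**The case against.** The strongest reply is that both texts can be obeyed at once. Only the Study Procedures text is phrased as mandatory. The baseline section describes how long the lead-in should last, and does not say that a patient below 2000 IU/mL may start regardless of the other requirement. Anyone below 20 IU/mL satisfies both. The trial is also declared not multi-institutional, so there is no variation between sites, and every patient stays on HBV therapy whichever limit is used.

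Most of this stands, and it limits the consequence. It does not remove the contradiction: the protocol gives one term two numerical meanings and states no order of precedence. That the stricter limit prevails is a sensible inference, but it is not written down.

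A reader might also infer several stronger points that the documents do not support:

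- *Already-treated patients have no limit.* The baseline section gives none for them, but the Study Procedures wording is general and contains no exemption.
- *HBV DNA is missing at screening.* For patients started on a nucleos(t)ide for this study, "the medication will be administered under this protocol after the consent has been signed and eligibility is determined". A limit to be met on that treatment would not be expected at screening.
- *Table 1 has no baseline sample.* The cell appears blank, but columns may have shifted when the PDF was read, and the baseline admission list includes viral kinetics.
- *A qualitative test would suffice.* The laboratory section mentions qualitative testing, but the design overview specifies quantitative HBV DNA during therapy, Study Procedures speaks of viral loads, and both limits are numeric.
- *A 0-hour sample would report too late.* No assay turnaround time is given.

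**Conclusion.** The contradiction is real and should be corrected. Two current sections define adequate HBV suppression before study drug with limits 100-fold (2 log10) apart. They give opposite answers for a newly treated patient at 20 to 1999 IU/mL.

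Its weight is modest. A reader might infer that the looser limit would distort the primary endpoint, a fall in HDV RNA of more than 2 log at week 24. The documents do not show this. Their background evidence on nucleos(t)ides and HDV RNA is mixed: lamivudine had no effect, while long-term tenofovir was followed by a reduction in 19 HIV/HDV patients. It also does not address the HBV DNA level at the start of HDV therapy. Nor do the documents show that any patient would in fact be dosed in the disputed band.

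The conclusion rests on two points. Both sections are read as current text describing the same step, which their wording supports. The statement that nothing settles precedence covers only the text available for review, from which a few pages had been removed. No view is taken on which limit is appropriate.

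**What to change.** - Reconcile the Hepatitis B Treatment text under Study Procedures with Baseline Evaluation and Initiation of Treatment, so that both state one threshold, chosen by the sponsor, in identical words.
- Record, before the first dose, the quantitative HBV DNA value that meets the threshold and the date of its sample.

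The cost is a short edit to two sections and one recorded value with its date. HBV DNA testing at the Clinical Center is already planned, and Study Procedures already has HBV viral load followed at each outpatient visit once the nucleos(t)ide has started. Sample size and analysis are unaffected.

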## LABORATORY PROCEDURES/EVALUATIONS

- **Baseline Labs** - prothrombin time (PT/INR), partial thromboplastin time (PTT), reticulocyte count, plasma haptoglobin level, anti-HBc.
- **Routine Labs** - complete blood count (CBC with differential), acute care panel (sodium, potassium, chloride, bicarbonate, creatinine, glucose, urea nitrogen, eGFR ), mineral panel (albumin, calcium, magnesium, phosphorus), hepatic panel (alkaline phosphatase, ALT, AST, total bilirubin, direct bilirubin), lipid panel (total cholesterol, triglycerides, HDL, LDL), LDH, CK, serum uric acid and total protein, urinalysis.
- **Monthly Labs** - PT, thyroid panel, pregnancy test
- **Serology Labs** - HBsAg, anti-HBs, HBeAg, and anti-HBe, anti-HDV, quantitative HBsAg levels.
- **Pancreatitis Monitoring:** amylase, lipase
- **Viral Kinetic and Pharmacokinetic Assessment (VK and PK):** includes HDV RNA and HBV DNA qualitative tests via polymerase chain reaction assay (PCR) or a quantitative PCR (qPCR) for viral titer. One red top tube (10 mL) will be obtained and stored in -80 for pharmacokinetic (PK) analysis of lonafarnib, ritonavir and lambda.

- **Reproductive Panel** - In males, AM levels of inhibin B, luteinizing hormone (LH), total and free testosterone, and follicle stimulating hormone (FSH) will be obtained. In females, AM levels of luteinizing hormone (LH), estradiol, progesterone, antimullerian hormone, follicle-stimulating hormone (FSH), dehydroepiandrosterone (DHEA), dehydroepiandrosterone sulfate (DHEAS), testosterone, sex hormone binding globulin (SHBG) and 17-hydroxyprogesterone (17-OHP) will be obtained.
- **Immunological Studies** - 30 - 50 ml of whole blood will be collected for immunological studies at specified time points described in table 1. 5 mm of liver tissue at baseline and end of therapy will also be collected for immunological studies, provided sufficient liver tissue is available after the required amount is obtained for histopathology. An additional pass will not be performed to obtain additional tissue for immunological studies.
- **Research Blood for Storage** - 7 ml of serum will be collected and stored at -80° C in the NIDDK clinical core lab.

**Fecal Microbiome and Bacterial Translocation (BT) analysis** - we plan to utilize pyrosequencing techniques to survey microbial diversity in patients' fecal samples. Patients may refuse the microbiome portion of the study and still participate in other portions of this study. Prior to stool sample collection, all the patients will continue their routine diets. At each visit, a specific medication history (including prescription and OTC medications) and dietary recordings (appendix 2) will be taken. Samples (stool and serum) will be elicited at the time points shown in Table 2 and stored in -80C for future analysis.

## **SPECIMEN PREPARATION, HANDLING AND STORAGE**

When appropriate, blood will be drawn in pediatric tubes and the amount of blood that will be drawn from adult patients (i.e., those persons 18 years of age or older) for research purposes shall not exceed NIH Clinical Center rules over any eight-week period.

- **HDV RNA** testing will be done by quantitative PCR. Quantification will be performed at The Doctors Laboratories (TDL). TDL has performed the HDV RNA quantification for previous lonafarnib studies including LOWR-1 through LOWR-4 and the LIMT (lambda interferon for HDV) study. There currently is a lack of standardization across available HDV RNA quantitative assays and no commercially approved assay exists in the United States. The lower limit of quantification (LLOQ) for this test is 14 IU/mL and the limit of detection (LOD) is 2 IU/mL . If the test does not detect the virus, the result will be reported as “<LLOQ, target not detected.” If the test detects the presence of the virus but was not able to accurately quantify the number of copies, the result will be reported as “<LLOQ, target detected.”.
- **HBV DNA** will be tested at the NIH Clinical Center utilizing the COBAS Ampliprep/COBAS Taqman HBV v2.0 test, which is an FDA approved assay intended for the use as an aid in the management of chronic HBV infection.

- **Resistance monitoring** will include determination of baseline isolate sequence analysis to enable identification and monitoring of changes in viral genome sequences as a function of treatment duration. Analysis of drug-treated patients will enable an assessment of background genomic variability. Any clinical evidence of breakthrough or rebound (defined as a greater than 1 log increase above an observed viral load nadir or HDV RNA that becomes quantifiable following a reduction to <LLOQ, target not detected) will prompt a more in-depth analysis that will focus first on the region encoding the CXXX box, as changes in the prenylation substrate sequence represent a logical potential mechanism of escape from prenylation-inhibiting drugs such as lonafarnib. Because other unanticipated mechanisms of resistance could theoretically be operative, however, we would anticipate also performing full genome sequencing to enable maximally unbiased assessment for candidate resistance mutations. Samples for analysis of potential host polymorphisms in the farnesyl transferase gene will be collected from all subjects. We will also have the ability to engineer any identified candidate resistance mutation back into an HDV vector competent for in vitro replication, in order to confirm that the mutation is indeed causative of any suspected decreased sensitivity to lonafarnib.
- **Immunological Studies** –
  - Chronic delta hepatitis is characterized by a lymphomononuclear infiltrate of the liver. The relative composition of this cellular infiltrate (HDV-specific T cells versus HBV-specific T cells versus nonspecific bystander cells), the antigenic targets within HDV that are recognized by these T cells and the contribution of the HDV-specific T cell response to disease progression are not known.
  - We aim to define the HDV-specific T cell response in blood samples of HDV/HBV-coinfected patients in the chronic stage of disease prior to treatment. Peripheral blood mononuclear cells (PBMC) will be isolated from blood samples. The HDV-specific CD4 and CD8 T cell response to recombinant delta antigen will be assessed by measuring cytokines (IFN $\gamma$ , TNF $\alpha$ , IL-2) by multicolor flow cytometry and enzyme-linked immunospot assays. Individual responses will be mapped with 41 overlapping peptides spanning the delta antigen and minimal optimal epitopes will be defined. The quality and strength of the HDV-specific T cell response will be compared to the quality and strength of the HBV core and surface antigen-specific response.
  - We also plan to take advantage of the fact that the prenylation inhibitor is a potent antiviral drug with no direct effect on the immune system. We will also evaluate whether a reduction of HDV viral or antigen load determined by treatment with the prenylation inhibitor causes a qualitative or quantitative change of the T cell response in the peripheral blood, and specifically, the emergence of HDV-specific memory T cells that we have identified in a rare case of a patient who spontaneously recovered from HDV infection ([name], [name], unpublished).

- Fecal Microbiome and Bacterial Translocation (BT)** Bacterial DNA will be extracted from patient serum and stool using QIAamp DNA mini kit (Qiagen) according to the manufacturer's protocol. Patients' dietary history of the day prior to stool sample collection and any changes made in medication use since screening visit will be recorded. Polymerase chain reaction (PCR) for a conserved region of the 16S rRNA gene will be performed with two universal primers, forward primers (27F-Bac, 5'-AGAGTTTGATCMTGGCTCAG-3') and reverse primers (543R-Bac, 5'-ATTACCGCGGCTGCTGGC-3') to detect and identify the bacterial DNA. For each sample, uniquely barcoded universal primers will be used for multiplexing. Amplified PCR products will be analyzed by agarose gel electrophoresis and then be pooled for pyrosequencing. Amplicons will undergo deep sequencing to be performed at SAIC-Frederick Inc. Sequences with a minimum length of 200 bp will be analyzed using mothur (version 1.21.0) for 16S rRNA gene sequence analysis. Taxonomic classification will be done using the RDP Classifier and phylogenetic tree will be generated using the Clearcut program. Blood will be drawn and used to measure microbial cell wall products, (LPS, peptidoglycan and beta-D-glucan), host response markers and selected cytokines.

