### ***Peginterferon lambda therapy in chronic viral hepatitis***

IFN-lambda is a type III of IFN with different structural features, receptor characteristics, and biological activities than IFN- $\alpha$  (Type I). IFN-lambda was first reported in the early 2000s. IFN-lambda and IFN- $\alpha$  share the common interferon-stimulated gene (ISG) induction pathway that leads to broad-spectrum antiviral activities (Figure 9). The biological activity of Lambda is derived from its recombinant human IFN  $\lambda 1$  moiety. Lambda binds to the human Type III IFN receptor leading to receptor dimerization. Receptor dimerization activates multiple intracellular signal transduction pathways initially mediated by the JAK/STAT (Janus kinase/signal transducer and activator of transcription) pathway.

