## **STUDY PROCEDURES AND SCHEDULE**

This is an open-label clinical trial treating 26 adult patients with chronic delta hepatitis with lonafarnib plus ritonavir and lambda interferon for 24 weeks. Patients will undergo baseline testing including blood draws, imaging, safety consults, and liver biopsy with portal pressure measurements prior to starting therapy. During therapy, all patients will be monitored with quantitative HDV RNA and HBV DNA levels as well as routine safety measures and liver function tests. After 24 weeks, therapy will be stopped and patients will again undergo repeated testing including blood draws, imaging, and safety consults. After stopping therapy, patients will be followed for an additional 24 weeks. At the end of the 24 weeks of post-therapy follow-up, patients will be re-admitted to the NIH Clinical Center and will undergo repeat testing including blood draws, imaging, as well as a transjugular liver biopsy with hepatic venous pressure gradient measurements.

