### **Immunologic Analysis**

Chronic delta hepatitis is characterized by a lymphomononuclear infiltrate of the liver. The relative composition of this cellular infiltrate (HDV-specific T cells versus HBV-specific T cells versus nonspecific bystander cells), the antigenic targets within HDV that

are recognized by these T cells and the contribution of the HDV-specific T cell response to disease progression are not known.

We aim to define the HDV-specific T cell response in blood samples of HDV/HBV-coinfected patients in the chronic stage of disease prior to treatment. Peripheral blood mononuclear cells (PBMC) will be isolated from blood samples. The HDV-specific CD4 and CD8 T cell response to recombinant delta antigen will be assessed by measuring cytokines (IFN $\gamma$ , TNF $\alpha$ , IL-2) by multicolor flow cytometry and enzyme-linked immunospot assays. Individual responses will be mapped with 41 overlapping peptides spanning the delta antigen and minimal optimal epitopes will be defined. The quality and strength of the HDV-specific T cell response will be compared to the quality and strength of the HBV core and surface antigen-specific response.

We also plan to take advantage of the fact that the prenylation inhibitor is a potent antiviral drug with no direct effect on the immune system. We will also evaluate whether a reduction of HDV viral or antigen load determined by treatment with the prenylation inhibitor causes a qualitative or quantitative change of the T cell response in the peripheral blood, and specifically, the emergence of HDV-specific memory T cells that we have identified in a rare case of a patient who spontaneously recovered from HDV infection ([name], [name], unpublished).

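### With lonafarnib, ritonavir and interferon lambda started together in one arm, the T-cell analysis cannot show that HDV reduction from the prenylation inhibitor causes immune change

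*Combined protocol and SAP*

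**What the plan says.** The immunology text appears twice, under Specimen Preparation, Handling and Storage (Immunological Studies) and under Immunologic Analysis. Both versions have two aims. The first is to characterise HDV-specific T cells before treatment. The second starts from the premise that the "prenylation inhibitor is a potent antiviral drug with no direct effect on the immune system", and then asks whether a fall in HDV viral or antigen load "determined by treatment with the prenylation inhibitor causes a qualitative or quantitative change of the T cell response". Neither version mentions lambda.

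The regimen is set out under Initiation of Treatment and is the same for everyone: "All patients will be initiated on lonafarnib 50 mg orally twice daily, ritonavir 100 mg orally twice daily and lambda 180 mcg subcutaneously weekly". Study Procedures and Schedule describes a single group: "This is an open-label clinical trial treating 26 adult patients with chronic delta hepatitis with lonafarnib plus ritonavir and lambda interferon for 24 weeks". There is no arm without lambda, no lead-in on lonafarnib and ritonavir, and no staggered start.

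On lambda's mechanism, the background section on peginterferon lambda says: "Receptor dimerization activates multiple intracellular signal transduction pathways". It places lambda on the same interferon-stimulated gene pathway as interferon alpha.

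**The concern.** The second aim is a causal chain with two links: the prenylation inhibitor lowers HDV, and lower HDV changes T cells. The neutrality premise is there to protect the second link. If the only active drug has no immune effect of its own, T-cell change can be read as a consequence of falling antigen.

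That argument would fit a trial of lonafarnib with ritonavir. Here lambda is given throughout, and it bears on both links. It may act on the immune response directly, and it lowers HDV itself. A report that followed the aim as written could claim that prenylation inhibition restores HDV-specific immunity, and the design would not support that. What is at stake is a mechanistic statement in an exploratory analysis. The efficacy and tolerability conclusions are not involved.

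**Working it through.** The aim has no sample size, power or test attached, so there is no planned figure to reproduce. The check is whether the planned data can identify what the aim asks.

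**Step 1: can the two drugs be separated?** Table 1 schedules immunology samples at baseline; 0 and 24 hours; weeks 4, 8 and 12; week 24; weeks 28, 32 and 36; and week 48. That is 1 + 2 + 3 + 1 + 3 + 1 = 11 time points. Code planned exposure as 0 or 1, with L for lonafarnib and M for lambda:

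| Time points | L | M |
|---|---|---|
| Baseline, 0 h (pre-dose) | 0 | 0 |
| 24 h, weeks 4, 8, 12, 24 | 1 | 1 |
| Weeks 28, 32, 36, 48 | 0 | 0 |

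In the model T = b0 + b1·L + b2·M + error, L = M in every row. The model reduces to T = b0 + (b1 + b2)·L + error. The correlation of L and M is 1.0, and the matrix [1, L, M] has rank 2 with 3 columns. Only the sum b1 + b2 is estimable. The visit lists give somewhat different immunology weeks from Table 1 (on treatment through week 20; post-treatment weeks 4, 8 and 16). The result is the same under either schedule, because the drugs start and stop together.

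**Step 2: first link, prenylation inhibitor to HDV decline.** The section on lambda in chronic HDV infection reports 6 of 10 patients (60%) with at least a 2-log decline, or below quantification, at week 24 on lambda alone. It also reports a 1.2-log fall in viremia in a mouse model. The background shows declines with lonafarnib and ritonavir as well. With two active components and no contrast between them, the decline belongs to the regimen.

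**Step 3: second link, antigen decline to T-cell change.** The link needs lambda's direct immune effect to be negligible. The documents do not say that it is, and three places point the other way:
- Lambda acts through JAK/STAT and induces interferon-stimulated genes.
- Exclusion criterion 10 covers autoimmune disease that lambda might worsen.
- Item 14 under Hazards and Discomforts reports an HBV study in which 6 patients met laboratory criteria for possible drug-induced liver injury, 4 + 1 = 5 of them on lambda. A host-mediated flare was the alternative explanation in 5 of the 6, so in at least 4 of the lambda cases.

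**Step 4: what remains estimable.** Step 1 contains no term for viral load. Across patients i, one can fit ΔT_i = a + b·ΔV_i + e_i, where ΔV is HDV decline. The intercept a absorbs the average effect of the regimen, lambda included, and b is estimable because declines will differ between patients. It is an association. Reading it causally requires that patients with larger declines did not also have stronger immune responses to lambda. The design cannot guarantee that, since lambda may drive both.

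**Step 5: do off-treatment samples help?** The end-of-therapy visit and Table 1 stop lonafarnib, ritonavir and lambda together at week 24. Item 10 under Hazards and Discomforts lists a rise in HDV load after therapy as a risk. From week 28 on, lonafarnib exposure, lambda exposure and possibly viral load have all changed at once, so the contrast isolates none of them.

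**The case against.** The case for leaving the text alone has several parts, and some of it stands.

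- **The protocol only asks a question.** True: it proposes to evaluate whether the reduction causes change. A reader might infer that the plan already attributes immune change to HDV decline, and the text does not go that far. But the question is causal, and its only stated support is the neutrality premise.
- **No effect of lambda on T cells is documented.** Also true. A reader might infer that lambda is known to alter T cells; the documents contain no such statement. The point needs less: the aim relies on excluding such an effect, and nothing in the protocol excludes it.
- **Confounding is not total.** A reader might infer that any T-cell change is wholly confounded and uninformative. That goes too far. The complete overlap in Step 1 applies to the planned exposure of the two drugs, not to viral-load decline, whose association with T-cell change can be estimated.
- **Exposure may diverge in practice.** A reader might infer that no patient can ever be on lonafarnib and ritonavir without lambda. Table 4 has neutrophil and platelet rules for lambda with no lonafarnib counterpart, so separate exposure is possible. The text before Table 3 speaks of discontinuing all three drugs, and the two places need reconciling. Any divergence would follow toxicity and would not identify the effect.
- **HBV-specific responses could serve as a within-patient comparator.** They are measured, but the comparison is described under the pre-treatment aim. Lambda also lowered HBV viremia in the mouse model, so the comparator is imperfect.
- **Little depends on it.** Agreed. Immunology is absent from the endpoints and from the statistical section.

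**Conclusion.** The point holds as a limit on inference. The design alone cannot credit HDV decline to the prenylation inhibitor, and it cannot attribute T-cell change to antigen decline rather than to lambda. The overlap is exact for planned lonafarnib and lambda exposure: identical at 11 of 11 time points. It does not extend to the association between T-cell change and the size of HDV decline.

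The conclusion rests on planned exposure, on the protocol's own report that lambda is active against HDV, and on the absence of any statement excluding a lambda immune effect. It does not assume that lambda changes T cells.

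The consequence is minor. The pre-treatment T-cell aim stands, and no endpoint, sample size or safety rule is affected.

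**What to change.** In both places where the second immunology aim appears:

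1. Delete the rationale that the prenylation inhibitor has no direct immune effect.
2. Restate the aim along these lines: *We will describe changes in T-cell response during and after treatment with lonafarnib, ritonavir and lambda, and estimate their association with the size of HDV decline across patients. No causal attribution to prenylation inhibition is intended.*
3. Keep the post-treatment samples as description only, and do not present them as a check on confounding.

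The association should be reported as an estimate with its confidence interval. With 26 patients planned and 30% dropout allowed for, about 18 (26 × 0.7 = 18.2) may be available, so precision will be limited.

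No visit, blood draw or patient is added. The cost is a weaker exploratory claim.
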